19.10. Missing Data

Given the mITT design, an imputation or some other procedure for handling missing primary endpoints is required.

For the primary efficacy endpoint, subjects who do not provide data to allow classification as responders will be considered nonresponders, that is, missing data will be imputed as “nonresponder”. A similar approach will be applied to secondary efficacy endpoints that are proportions.

For continuous secondary efficacy endpoints collected directly from the CRF, the method of last observation carried forward (LOCF) will be used to impute the missing values. For other continuous secondary efficacy endpoints that need to be derived based on patients’ response to a questionnaire, if the responses to an entire questionnaire are missing, LOCF will be applied; otherwise, the method of handling missing response is described in each individual section for the secondary efficacy endpoint analysis.

A full description of missing data imputation method for all endpoints will be described in the statistical analysis plan.

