16.2. Investigator (or Designee) and Blinded Rater Completed Assessments

The EDSS and FSS are to be completed by an appropriately trained blinded rater. The CGI-I assessment will be completed by an appropriately trained investigator or designee. When these assessments are required, they should be the done immediately after subject reported outcome/questionnaire completion (if applicable) and must be completed prior to any study drug dosing. The same trained rater should complete these assessments at all required time points for a subject.

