16.3. Clinical Global Impression of Improvement

The CGI-I was developed for use in clinical research to provide a brief overview of the change in a subject's global function compared to baseline and regardless of study drug treatment (Guy, 1976; Busner and Targum, 2007). It requires a rating from 1 (very much improved) to 7 (very much worse).

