19.2. Analysis Populations

- The Safety Population will include all randomized subjects who receive 1 or more doses of study drug.
- The Modified Intent-to-Treat (mITT) Population will include all enrolled subjects who receive 1 or more doses of study drug and who have at least 1 postbaseline EDSS score.
- The Per-Protocol Population will include the subset of the mITT population who complete the study as per protocol.

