19.3.3. Secondary Efficacy Endpoints

- The response rates on MSIS-29 and 90% CIs on Day 7, Day 14, Day 21 and Day 42 for each treatment group.
- The response rates on EDSS and 90% CIs on Day 7 and Day 21 for each treatment group.
- CGI-I mean scores and 90% CIs on Day 7, Day 21 and Day 42 for each treatment group.

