19.5. Efficacy Analysis

A responder on EDSS is defined as a subject who achieves the following:

- ≥ 1.0 point improvement on EDSS score compared to baseline if baseline EDSS score was ≤ 5.5 .
- ≥ 0.5 point improvement on EDSS score if the baseline EDSS score was > 5.5 .

A responder on MSIS-29 is defined as a patient who achieves ≥ 8 point improvement on the physical subscale score of MSIS-29 compared to baseline.

Baseline is defined as the value observed prior to first dose of the study drug (Day 1).

The primary efficacy endpoint, the response rate on EDSS at Day 42, will be calculated by treatment group. Response rates and 90% Wilson CIs will be reported for each treatment group. These analyses will be performed for the mITT and Per-Protocol populations.

Summary statistics (n, mean, SD, median, minimum, and maximum) of the baseline value, the value at each scheduled postbaseline evaluation and the corresponding change from baseline for EDSS score will be presented by treatment group for all subjects in the mITT population and the Per-Protocol population.

A subject-by-subject data listing sorted by treatment group and subsequently by subject will be generated for all subjects in the mITT population.

For the secondary endpoints, the response rate endpoints will be analyzed and presented with the same approach as described above for the primary efficacy endpoint. The mean score endpoint will be calculated by treatment group. Mean, SD, and 90% CI will be presented by treatment group. All secondary efficacy analyses will use the mITT population.

For the exploratory endpoints, scores change from baseline will be calculated by treatment group. Mean, SD, and 90% CI will be presented by treatment group. All exploratory efficacy analyses will use the mITT population.

For all efficacy endpoints, the normality assumption of the data will be examined using appropriate normality test. If the test result shows the data is not normally distributed, then median, 10% and 90% percentiles will be presented instead of mean, SD and 90% CI.

The statistical analysis plan will describe in further detail the analyses for primary, secondary, and exploratory efficacy endpoints.

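### LOCF for the CGI-I means can bias the Day 21 and Day 42 arm means, in either direction, and make their 90% CIs under-cover if ratings are missing while relapse symptoms are still changing

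*Combined protocol and SAP*

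**What the plan says.** Section 19.3.3 lists "CGI-I mean scores and 90% CIs on Day 7, Day 21 and Day 42 for each treatment group". The other secondary endpoints are response rates, which Section 19.10 handles by counting missing as nonresponse. The LOCF sentence, "the method of last observation carried forward (LOCF) will be used to impute the missing values", therefore applies to CGI-I alone. CGI-I belongs to the class taken directly from the CRF because it is rated by site staff (Section 16.2: "The CGI-I assessment will be completed by an appropriately trained investigator or designee"). The scale runs from 1 (best) to 7 (worst), so lower is better (Section 16.3).

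For the mean score, Section 19.5 states "Mean, SD, and 90% CI will be presented by treatment group" and "All secondary efficacy analyses will use the mITT population". The mITT set needs one dose and is limited to subjects "who have at least 1 postbaseline EDSS score" (Section 19.2), so a subject who misses later visits stays in and is filled. If a normality test fails, "then median, 10% and 90% percentiles will be presented instead of mean, SD and 90% CI" (Section 19.5).

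Section 14.6 schedules CGI-I at early termination as well as at Day 42. Table 1 has no CGI-I at Baseline or Day 14. Section 19.10 leaves the full description of imputation to a separate statistical analysis plan, which is not among the documents reviewed. They state no missing-data assumption and no sensitivity analysis for CGI-I.

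**The concern.** LOCF assumes that nothing changes after the last rating. Section 9.1 describes relapses as followed by partial or complete recovery, and the sample-size section expects Day 42 EDSS response in 60% of the Acthar arm and 25% of the placebo arm. A flat course after Day 7 fits poorly with that premise. Dosing lasts 14 days, so a Day 7 rating carried to Day 42 presents a mid-treatment value as the outcome four weeks after dosing ends.

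Withdrawal can also be related to outcome. Sections 15.3.1 and 21.1 treat subjects who have plasma exchange or IVIg for lack of efficacy as treatment failures and withdraw them. Under LOCF such a subject keeps the last CGI-I rating, which may predate later worsening.

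At stake is how well the arm-level CGI-I means and CIs describe Day 21 and Day 42, in a pilot meant to inform a larger trial.

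**Working it through.** **Inputs from the documents.** 30 mITT subjects per arm (Section 19.9); CGI-I at Days 7, 21 and 42; 90% CI by arm, taken as two-sided; LOCF.

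**Inputs assumed, because the documents do not give them.** CGI-I SD 1.0; correlation 0.5 between Day 7 and Day 42; share p of Day 42 ratings carried from Day 7; mean change d after the carried rating. The main range is p = 10% to 20% and d = 0.5 to 1.0.

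**1. The plan's own figures.** None is given for CGI-I. The EDSS intervals confirm the working n of 30: the 90% Wilson interval for 18/30 is (45.06%, 73.29%), matching the stated 60% case. The stated placebo interval matches 8/30, which gives (15.73%, 41.46%), rather than exactly 25%. This does not affect the CGI-I point.

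**2. Bias in the arm mean** = p × d.
- p = 10%: 0.10 × 0.5 = 0.05; 0.10 × 1.0 = 0.10
- p = 20%: 0.20 × 0.5 = 0.10; 0.20 × 1.0 = 0.20

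With d = 0 the bias is 0. If subjects improve after the carried rating, the LOCF mean is too high and the arm looks worse. If they worsen, it is too low and the arm looks better.

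**3. Interval width.** Half-width = t × SD / √n. At SD 1.0 this is 0.310 for n = 30, 0.328 for n = 27 and 0.350 for n = 24. Counting 30 values when 27 or 24 were observed gives ratios of 0.945 and 0.887, but only if the SD is unchanged. Carried ratings lying d away from the rest inflate the SD to about √(1 + p(1 − p)d²). For p = 10% and d = 1.0 that is √1.09 ≈ 1.04, and the ratio becomes 0.945 × 1.04 ≈ 0.99.

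**4. Coverage of the nominal 90% interval.** Simulation: n = 30, 20,000 runs, normal data, missing completely at random, Day 7 carried to Day 42.

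| Share carried | Later change | Bias | LOCF half-width | Ratio to observed-case width | LOCF coverage |
|---|---|---|---|---|---|
| 10% | 0 | 0.00 | 0.308 | 0.945 | 90.3% |
| 10% | 0.5 | 0.05 | 0.311 | 0.955 | 88.9% |
| 10% | 1.0 | 0.10 | 0.321 | 0.986 | 85.9% |
| 10% | 1.5 | 0.15 | 0.337 | 1.035 | 82.1% |
| 20% | 0 | 0.00 | 0.308 | 0.885 | 90.3% |
| 20% | 0.5 | 0.10 | 0.313 | 0.905 | 85.3% |
| 20% | 1.0 | 0.20 | 0.331 | 0.955 | 74.5% |

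At zero change the LOCF interval is at its narrowest relative to observed cases, yet it covers at 90%. At 10% carried and a 1.5-point change it is the wider of the two, yet it covers at 82.1%. The loss of coverage follows the shift in the centre, not the width. Observed-case coverage was about 90% throughout, but only because the simulated data were missing completely at random. That says nothing about withdrawal for lack of efficacy.

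**5. Normality rule.** The plan names no test. On samples of 30 from three assumed 7-point distributions, Shapiro-Wilk rejected normality in 92% to 95%. The planned CGI-I mean and CI could therefore often give way to a median and percentiles.

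**The case against.** The strongest case against the point is that its size rests wholly on assumed inputs, and several provisions limit it.

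- **Exit ratings.** CGI-I is collected at early termination, and Section 21.1 sends withdrawn subjects through the assessments of Sections 14.5 and 14.6, both of which list CGI-I. For many dropouts the carried value would be an exit rating rather than a Day 7 one. This stands: it reduces the bias when the exit rating is close to Day 42, though the rating is still frozen at exit. The three subjects per arm lost in Section 19.9 are lost before mITT entry, so they do not support a 10% to 20% rate.
- **Normality rule.** The mean and CI may not be the reported summary. This stands, and the figures above would not then apply. The median and percentiles would still use the filled data unless the plan says otherwise.
- **Deferred detail.** A sensitivity analysis may appear in the separate plan. That is possible, but it would not undo a rule that Section 19.10 already states.
- **The remedy's own assumption.** A mixed model assumes missing at random, which withdrawal for lack of efficacy strains. This stands, so the remedy needs a companion analysis.

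Two stronger readings are tempting. A reader might infer that LOCF makes the CIs too narrow because imputed values are counted as data. The calculations do not support that in general: where the narrowing is greatest, with no later change, coverage is nominal, and with a large change the interval can be wider than the observed-case one. A reader might also infer that nonresponder imputation for EDSS alongside LOCF for CGI-I is a contradiction. It is not, since nonresponder imputation has no direct counterpart for a mean score and Section 19.10 sets out the split openly.

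**Conclusion.** The point holds in conditional form. LOCF is the stated rule for CGI-I and, within the documents, the only one. It can bias the Day 21 and Day 42 means, in either direction, and lower the coverage of their 90% CIs when ratings are missing and symptoms change after the last one. Under the main assumed range the Day 42 bias is 0.05 to 0.20 points, about 16% to 64% of a 0.31 half-width, with simulated coverage from 88.9% down to 74.5%. At 5% carried and the same changes it is only about 0.03 to 0.05 points.

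The documents do not support saying that bias will occur, which way it will go, or that it will differ by arm, because they give neither the missing-visit rate nor the later change. The consequence is modest: CGI-I is secondary, no between-arm test is planned, and the primary EDSS response rate does not use LOCF. This is a low-cost improvement, not a flaw that threatens the study.

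**What to change.** Amend Section 19.10 and carry the same text into the separate analysis plan, which Section 19.1 says is finalized before database lock:

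1. **Main CGI-I analysis.** Fit a mixed model for repeated measures to the observed ratings at Days 7, 21 and 42, with arm, visit, arm-by-visit and an unstructured covariance. Report the model mean and 90% CI with the observed n, per arm and visit. State the missing-at-random assumption.
2. **LOCF.** Keep it as a sensitivity analysis only.
3. **Treatment failures.** Add a sensitivity analysis that gives subjects withdrawn as treatment failures under Sections 15.3.1 and 21.1 an unfavourable CGI-I rating, fixed in advance, at visits after withdrawal.
4. **Normality rule.** State how the Section 19.5 rule applies to a 7-point rating, including whether it replaces the model mean and CI and which data any median and percentiles use.
5. **Details.** Say how a missing Day 7 rating is handled, since there is no earlier CGI-I to carry, and how early-termination ratings are assigned to visits.

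The cost is plan text and a standard model, with no new data. The price is reliance on missing at random, which item 3 probes, and possibly slightly wider intervals.

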19.11. Deviations From the Statistical Analysis Plan

Any deviations from the planned statistical analysis will be described and justified in the final clinical study report as appropriate.

20. ADVERSE EVENTS AND SERIOUS ADVERSE EVENTS

20.1. Safety

For safety information about Acthar, refer to the most recent version of the Prescribing Information (Mallinckrodt, 20159).

20.2. Definitions

Adverse Event

An AE is any untoward or undesirable medical occurrence in a subject who is administered an IMP, which does not necessarily have to have a causal relationship with this treatment.

Examples of AEs include but are not limited to:

- Clinically significant laboratory findings.
- Clinically significant changes in physical examination findings.
- An AE occurring due to IMP overdose whether accidental or intentional.
- An AE occurring from IMP abuse.
- An AE associated with IMP withdrawal.
- Unexpected Adverse Event.

An unexpected AE is defined as an AE, the nature and severity of which is not consistent with the applicable product information in the most recent version of Acthar Package Insert ([Mallinckrodt, 2019](#)).

Serious Adverse Event

An SAE is defined as any untoward medical occurrence that results in any of the following outcomes:

- Death.
- A life-threatening AE.
- Inpatient hospitalization or prolongation of existing hospitalization.
- A persistent or significant incapacity or substantial disruption of the ability to conduct normal life functions.
- Results in a congenital anomaly/birth defect.

Important medical events that may not result in death, be life-threatening, or require hospitalization may be considered serious when, based upon appropriate medical judgment, may jeopardize the subject or subject and may require medical or surgical intervention to prevent one of the outcomes listed above. Examples of such medical events include allergic bronchospasm requiring intensive treatment in an emergency department or at home, blood dyscrasias or convulsions that do not result in inpatient hospitalization, or the development of drug dependency or drug abuse.

Death

Death is an outcome of an event. The event that resulted in death should be recorded and reported on the SAE Form. All causes of death must be reported as SAEs. The investigator should make every effort to obtain and send death certificates and autopsy reports to Mallinckrodt.

Life-Threatening Event

A life-threatening event refers to immediate risk of death as the event occurred per the reporter. A life-threatening event does not include an event that, had it occurred in a more severe form, might have caused death but, as it actually occurred, did not create an immediate risk of death. For example, hepatitis that resolved without evidence of hepatic failure would not be considered life-threatening, even though hepatitis of a more severe nature can be fatal. Similarly, an allergic reaction resulting in angioedema of the face would not be life-threatening, even though angioedema of the larynx, allergic bronchospasm, or anaphylaxis can be fatal.

Hospitalization

Hospitalization is defined as an official admission to a hospital. Hospitalization or prolongation of a hospitalization constitutes a criterion for an AE to be serious; however, it is not in itself considered an SAE. In absence of an AE, a hospitalization or prolongation of a hospitalization should not be reported by the investigator as an SAE. Such situations include, but are not limited to, the following:

A hospitalization or prolongation of hospitalization is needed for a procedure required by the protocol.

A hospitalization or prolongation of hospitalization is part of a routine procedure followed by the center (eg, stent removal after surgery). This should be recorded in the study file.

A hospitalization for a preexisting condition that has not worsened.

Note that the following hospitalizations are not considered SAEs in Mallinckrodt clinical studies:

A visit to the emergency department or other hospital department of less than 24 hours that does not result in admission (unless considered "important medical event" or life-threatening event).

20.3. Adverse Event and Serious Adverse Event Classifications

Study Drug Relatedness

The following classifications should be used when evaluating the relationship of AEs or SAEs to study treatment ([Table 2](#)).

Table 2: Adverse Event Relationships

Relationship	Definition
Not Related	No relationship between the experience and the administration of study treatment; related to other etiologies such as concomitant medications or subject's clinical state.
Unlikely Related	The current state of knowledge indicates that a relationship is unlikely.
Possibly Related	A reaction that follows a plausible temporal sequence from administration of the study treatment and follows a known response pattern to the suspected study treatment. The reaction might have been produced by the subject's clinical state or other modes of therapy administered to the subject.
Related	A reaction that follows a plausible temporal sequence from administration of the study treatment and follows a known response pattern to the suspected study treatment and can be confirmed with a positive re-challenge test or supporting laboratory data.

Severity Assessment

For purposes of consistency, if required the investigator may use the intensity grades presented in [Table 3](#).

Table 3: Adverse Event Severity Grades

Grade	Definition
Mild	Does not interfere with subject's usual function and activities
Moderate	Interferes to some extent with subject's usual function and activities
Severe	Interferes significantly with subject's usual function and activities

If an AE increases in severity (eg, from moderate to severe); decreases in severity (eg, changes from moderate to mild); or there is a change in seriousness, a new AE will be opened and the original AE will be closed. If an AE is still ongoing at the time of a subject's completion of the follow-up visit, the resolution/stop date and time is left blank.

To ensure there is no confusion or misunderstanding of the difference between the terms "serious" and "severe," which are not synonymous, the following note of clarification is provided:

The term "severe" is used to describe the intensity (severity) of a specific event (as in mild, moderate, or severe myocardial infarction); the event itself, however, may be of relatively minor medical importance (such as a severe headache). This is not the same as "serious," which is based on the subject/event outcome or action criteria usually associated with events that pose a threat to a subject's life or functioning. Seriousness (not severity) serves as a guide for defining regulatory reporting obligations.

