15.3.1. Treatment Discontinuation

Treatment with study drug should be discontinued if any of the following occur:

- Development of accelerated hypertension (defined as systolic blood pressure \geq 180 *and* diastolic blood pressure \geq 100 mm Hg) that cannot be managed by the adjustment of concomitant medications such as antihypertensive medications.
- Development of congestive heart failure that cannot be managed by the adjustment of concomitant medications such as diuretics and antihypertensive medications.
- Development of diabetic signs/symptoms (ie, HbA1c $>$ 6.5%, or fasting plasma glucose $>$ 126 mg/dL, or classic symptoms of hyperglycemia with random plasma glucose $>$ 200 mg/dL).
- Subjects who undergo plasma exchange or IVIg due to lack of efficacy will be considered treatment failures and will be withdrawn from the study.
- Development of any other AE of at least moderate intensity and possibly, probably or definitely related to study drug that cannot be managed by the adjustment of concomitant medications.

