20.4. Adverse Event and Serious Adverse Event Recording and Reporting

AEs and SAEs will be recorded from signing of the ICF through completion of the final study visit. The investigator is required to record the AE or SAE regardless of the severity of the event or its relationship to study treatment. Prior to the Baseline Visit/Day 1, only AEs and SAEs related to study procedures will be recorded. The investigator must follow up on all AEs and SAEs reported until the event has resolved or stabilized or at such time the

investigator refers the subject to a nonstudy physician. The investigator will document the further follow-up information in the subject's source document.

During the period specified above, the investigator will:

Record all AEs and SAEs from the signing of the ICF through the completion of the End of Study/Early Termination visit.

Report all SAEs on an SAE Report Form to Global Pharmacovigilance or designee.

Report all pregnancies to the Global Pharmacovigilance or designee contact-on the Pregnancy Surveillance Form.

Submit any Expedited Safety Report or Suspected Unexpected Serious Adverse Reaction from Global Pharmacovigilance or designee to the IRB/IEC.

The reporting requirements for AEs are summarized in [Table 4](#).

Table 4: Reporting Requirements for Adverse Events

Seriousness	Reporting Time	Type of Report
All Serious	Within 24 hours of first knowledge of event	Initial report on the SAE Form, appropriate eCRF, and source document
	Within 24 hours of receipt of follow-up information	Follow up report on the SAE Form, appropriate eCRF, and source document
Nonserious	Per case report form submission procedure	Appropriate eCRF and source document

Adverse Events

Adverse events can be reported spontaneously or elicited during open-ended questioning (ie, "How have you been feeling since your last visit?"), examination, or evaluation of a subject. Signs and symptoms must be recorded using standard medical terminology. For subjects incapable of giving consent, the legally acceptable representative may provide information regarding the subject's status.

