20.5. Adverse Events of Special Interest

AEs of special interest for this study are outlined below. Adverse events of special interest will be followed until resolution or return to baseline.

- Elevated blood pressure (defined as systolic blood pressure ≥ 180 and diastolic blood pressure ≥ 100 mm Hg).
- Hyperglycemia (HbA1c $> 6.5\%$, or fasting plasma glucose > 126 mg/dL, or classic symptoms of hyperglycemia with random plasma glucose > 200 mg/dL).
- MedDRA System Organ Class infection/infestation of \geq moderate intensity.
- AEs considered possibly, probably, or definitely related to study drug treatment of \geq moderate intensity.
- Hy's Law cases (ALT > 3 x ULN, with total bilirubin > 2 x ULN, no initial signs of cholestasis [alkaline phosphatase within the reference range]), and no other reason can be found to explain liver injury).

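### Table 2 offers no positive relatedness grade for a plausibly timed adverse event of a wholly new type, and the two rules that turn on relatedness use a different scale

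*Combined protocol and SAP*

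**What the plan says.** Section 20.3 introduces its four-grade scale with "The following classifications should be used when evaluating the relationship of AEs or SAEs to study treatment". The rows of Table 2 are:

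- *Not Related*: no relationship, with the event put down to other causes.
- *Unlikely Related*: "The current state of knowledge indicates that a relationship is unlikely".
- *Possibly Related*: plausible timing and a reaction that "follows a known response pattern to the suspected study treatment. The reaction might have been produced by" the subject's clinical state or other treatment.
- *Related*: plausible timing and a reaction that "follows a known response pattern to the suspected study treatment and can be confirmed with a positive re-challenge test or supporting laboratory data".

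Three other places use study-drug relatedness. Section 19.6.1 summarises adverse events by relation to study drug. The last stopping bullet of section 15.3.1 reads "Development of any other AE of at least moderate intensity and possibly, probably or definitely related to study drug", and applies where the event cannot be managed by adjusting concomitant medication. The fourth adverse event of special interest (AESI) in section 20.5 covers "AEs considered possibly, probably, or definitely related to study drug treatment of" moderate or greater intensity. For AESIs the follow-up duty is: "Adverse events of special interest will be followed until resolution or return to baseline".

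**The concern.** A causality scale should let an investigator record suspicion about an unfamiliar reaction. Here both positive grades depend on the reaction being already recognised. An event that starts at a plausible time after dosing, has no established other cause and resembles nothing known for the drug meets neither definition.

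Safety and tolerability is a primary objective (section 10.1), and the open-ended entries in sections 15.3.1 and 20.5 are there to catch events nobody listed in advance. If they are read through Table 2, they are closed to the least familiar reactions. At stake are the grade under which such an event appears in the by-relationship summary, whether it triggers the relatedness-based stopping bullet, and whether it gets the longer AESI follow-up.

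The mismatch in terms is a second, related problem. Sites must translate a four-grade scale into rules written for another scale, and the protocol does not say how.

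**Working it through.** No arithmetic beyond counting applies. The texts are set side by side.

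**Step 1: which grades can a plausibly timed, wholly new reaction take?**

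| Table 2 grade | Condition | Met by such an event? |
|---|---|---|
| Related | timing + known pattern + confirmation | No, the pattern is not known |
| Possibly Related | timing + known pattern; another cause may explain it | No, the pattern is not known |
| Unlikely Related | current knowledge points against a link | Not cleanly; lack of precedent is not evidence against a link |
| Not Related | no relationship; other cause | Not cleanly; no other cause is established |

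Positive grades: 2 of 4. Positive grades requiring a known pattern: 2 of 2. The event has no positive grade and no well-fitting grade. Because section 20.3 directs that the table be used, literal application leaves only a non-positive grade.

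**Step 2: which rules could this reach?**

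Section 15.3.1 has 5 bullets: accelerated hypertension, congestive heart failure, diabetic signs or symptoms, plasma exchange or IVIg for lack of efficacy, and any other adverse event subject to a relatedness test. Four name a specific condition or event. The 1 of 5 left open carries the relatedness test.

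Section 20.5 has 5 items: blood pressure, hyperglycaemia, infections of at least moderate intensity, related adverse events of at least moderate intensity, and Hy's Law cases. Again 1 of 5 turns on study-drug relatedness. The infection item spans a whole System Organ Class with no such test, so a new kind of infection of that intensity is an AESI whatever its grade.

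**Step 3: do the scales match?**

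Sections 15.3.1 and 20.5 use three terms: possibly, probably, definitely. Only the first has a counterpart in Table 2, so 2 of 3 are absent from it. Of Table 2's 2 positive grades, 1 ('Related') is named in neither rule. Neither rule cites Table 2.

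**Step 4: what would differ for an affected event?**

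An AESI is followed to resolution or return to baseline. For other events section 20.4 says "The investigator must follow up on all AEs and SAEs reported until the event has resolved or stabilized", or until referral to a nonstudy physician. Section 17.1 also ends follow-up at resolution or stabilisation and gives no referral exit. The difference is therefore mainly stabilisation against full resolution or return to baseline.

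**Step 5: who is outside the point?**

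An event that is unexpected only in its severity can still follow a known pattern and so can still be graded 'Possibly Related'.

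**The case against.** A reader might infer more: that new-type events will be down-graded to 'Unlikely Related' and so vanish from the related counts, the stopping bullet and the AESI list. The documents do not support that, for three reasons.

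- 'Unlikely Related' asks for knowledge that points against a link. Table 2 does not say where an unprecedented event goes, so naming that grade predicts investigator behaviour. An investigator might read 'known response pattern' broadly, at the level of ACTH or corticosteroid pharmacology, or grade the event 'Possibly Related' anyway.
- Section 19.6.1 does not define a pooled 'related' count. A summary by grade would still show the event in its own row, and section 19.1 leaves detail to a separate analysis plan.
- Sections 15.3.1 and 20.5 neither cite Table 2 nor use its scale. A site that takes 'possibly' in its ordinary sense would still catch the event.

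The safeguards are also substantial. All adverse events are recorded whatever their relationship (section 20.4). Serious events are reported within 24 hours even if they do not appear related (section 20.4). Treatment-emergent events are summarised by arm in a placebo-controlled, double-blind trial (section 19.6.1). The primary safety endpoint names no relatedness grade (section 19.3.2). Section 21.1 discontinues a subject for any adverse event judged an unacceptable risk. The scenario is also narrow: an approved product, within its labelled dose range, for 14 days, with 33 subjects planned per arm.

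All of this stands as a limit on impact. None of it gives the scale a suitable grade or reconciles the terms. A further objection is that leaving 'Related' unchanged keeps the known-pattern condition in one grade. That is true, but it does little harm, because 'Possibly Related' is enough to trigger both rules.

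**Conclusion.** The defect in Table 2 is plain on the text: no positive grade is open to a plausibly timed adverse event of a wholly new type, and no grade fits it cleanly. The mismatch with sections 15.3.1 and 20.5 is equally plain.

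The consequences are conditional. If those two rules are read through Table 2, an event of moderate or worse intensity that is not otherwise listed would fail the last bullet of section 15.3.1 and the fourth item of section 20.5. The section 19.6.1 summary would show it under a non-positive grade. This assumes that investigators apply 'known response pattern' literally. If they do not, the likely result is inconsistent grading and inconsistent use of the two rules between sites.

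The impact is small, and the number of events affected cannot be derived from the documents. It would be wrong to conclude that new reactions go unrecorded, or that the overall comparison of adverse events between arms is compromised. Confidence is moderate: high for the wording, lower for its effect in practice.

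**What to change.** Make three wording changes.

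1. In Table 2, define 'Possibly Related' as plausible timing with a reasonable possibility that study treatment caused the event, whether or not the reaction is already known, and even if clinical state or another therapy might explain it.
2. Keep 'Related' as the stricter, confirmed grade.
3. In the last bullet of section 15.3.1 and the fourth item of section 20.5, replace the three-term phrase with 'Possibly Related or Related (Table 2)'.

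The cost is one grade definition, two bullets and a note in the case report form instructions. The downside is somewhat more events graded possibly related and followed as AESIs, in both arms.
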